APPENDIX 11. DOSE DE-ESCALATION DECISION TABLE USING THE mTPI METHOD

The table below will be used for decision making with regards to potential starting dose escalations in subsequent patients. The assessment is based on the number of patients with toxicity at a given dose regimen of sitravatinib in combination with pembrolizumab and enfortumab in the lead-in dose escalation evaluation (Cohort 9) as defined in [Appendix 9](#) and assumes a maximum toxicity level of no more than 30% at the tolerated dose. The letters in different colors are computed based on the decision rules under the mTPI-2 method ([Guo-2017](#)) and represent different dose-finding actions which include: E = Escalate to next higher dose; S = Stay at the current dose; D = De-escalate to the next lower dose; and U = The current dose is unacceptably toxic.

		Number of Patients Treated at Current Dose																													
		1	2	3	4	5	6	7	8	9	10	11	12	13	14	15	16	17	18	19	20	21	22	23	24	25	26	27	28	29	30
Number of Toxicities	0	E	E	E	E	E	E	E	E	E	E	E	E	E	E	E	E	E	E	E	E	E	E	E	E	E	E	E	E	E	
	1	D	D	D	S	E	E	E	E	E	E	E	E	E	E	E	E	E	E	E	E	E	E	E	E	E	E	E	E	E	
	2		DU	D	D	D	D	S	S	E	E	E	E	E	E	E	E	E	E	E	E	E	E	E	E	E	E	E	E	E	
	3			DU	DU	D	D	D	D	D	S	S	S	E	E	E	E	E	E	E	E	E	E	E	E	E	E	E	E	E	
	4				DU	DU	DU	D	D	D	D	D	D	S	S	S	S	E	E	E	E	E	E	E	E	E	E	E	E	E	
	5					DU	DU	DU	DU	DU	D	D	D	D	D	D	S	S	S	S	S	E	E	E	E	E	E	E	E	E	
	6						DU	DU	DU	DU	DU	DU	D	D	D	D	D	D	D	D	S	S	S	S	S	S	E	E	E	E	
	7							DU	DU	DU	DU	DU	DU	DU	DU	D	D	D	D	D	D	D	D	D	D	D	S	S	S	S	
	8								DU	DU	DU	DU	DU	DU	DU	DU	DU	DU	DU	DU	D	D	D	D	D	D	D	S	S	S	S
	9									DU	DU	DU	DU	DU	DU	DU	DU	DU	DU	DU	DU	D	D	D	D	D	D	D	D	S	S
	10										DU	DU	DU	DU	DU	DU	DU	DU	DU	DU	DU	DU	DU	DU	DU	DU	DU	DU	DU	DU	DU
	11											DU	DU	DU	DU	DU	DU	DU	DU	DU	DU	DU	DU	DU	DU	DU	DU	DU	DU	DU	DU
	12												DU	DU	DU	DU	DU	DU	DU	DU	DU	DU	DU	DU	DU	DU	DU	DU	DU	DU	DU
	13													DU	DU	DU	DU	DU	DU	DU	DU	DU	DU	DU	DU	DU	DU	DU	DU	DU	DU
	14														DU	DU	DU	DU	DU	DU	DU	DU	DU	DU	DU	DU	DU	DU	DU	DU	DU
	15															DU	DU	DU	DU	DU	DU	DU	DU	DU	DU	DU	DU	DU	DU	DU	DU
	16																DU	DU	DU	DU	DU	DU	DU	DU	DU	DU	DU	DU	DU	DU	DU
	17																	DU	DU	DU	DU	DU	DU	DU	DU	DU	DU	DU	DU	DU	DU
	18																		DU	DU	DU	DU	DU	DU	DU	DU	DU	DU	DU	DU	DU
	19																			DU	DU	DU	DU	DU	DU	DU	DU	DU	DU	DU	DU
	20																					DU	DU	DU	DU	DU	DU	DU	DU	DU	DU
	21																						DU	DU	DU	DU	DU	DU	DU	DU	DU
	22																							DU	DU	DU	DU	DU	DU	DU	DU
	23																								DU	DU	DU	DU	DU	DU	DU
	24																									DU	DU	DU	DU	DU	DU
	25																										DU	DU	DU	DU	DU
	26																											DU	DU	DU	DU
	27																												DU	DU	DU
	28																													DU	DU
	29																														DU
30																														DU	

E = Escalate to the next higher dose
 S = Stay at the current dose
 D = De-escalate to the next lower dose
 U = The current dose is unacceptably toxic
 MTD = 0.30
 Sample size = 30
 Epsilon1 (ε1) = 0.05
 Epsilon1 (ε2) = 0.03

APPENDIX 12. COVID-19 PANDEMIC CHANGES TO STUDY CONDUCT

The table below summarizes temporary changes to specific protocol assessments and procedures that are allowable during the COVID-19 pandemic ([FDA-2020](#)); these changes will not be recorded as protocol deviations unless otherwise specified. This appendix should be considered in effect until notification from Mirati is provided via Administrative Letter. Upon such notification, this appendix will no longer be applicable, and study conduct in accordance with the language in the body of the protocol will resume.

Patients should not be enrolled into the lead-in dose escalation portion of Cohort 9 unless they are able to meet the protocol defined assessments and procedures including adhering visit windows.

Assessment/Procedure	Change During COVID-19 Pandemic
Visit Window	
 • Visit widows of up to +/- 5 days are allowed for Day 1 (beyond Cycle 1) and Day 15 clinic visits. • Visit windows of +/- 3 days are allowed for Day 8 clinic visits (for dose expansion portion of Cohort 9 and Cohort 10).
Clinic Visits	
 • Clinic visits may be conducted remotely by telephone/video conference; any missed assessments or procedures (e.g., tumor assessment, laboratory assessments, vital signs, study drug administration, etc.) should be documented as Protocol Deviations. • Clinic visits may be conducted at the patient's residence by qualified home health care professionals; any missed assessments or procedures (e.g., laboratory assessments, vital signs, study drug administration, etc.) should be documented as Protocol Deviations.
Safety Laboratory Assessments	Safety laboratory assessments may be performed at the patients nearest CAP or CLIA certified local laboratory if a remote visit is being conducted, whenever feasible.
Nivolumab Dosing (for Cohorts 1 through 8)	
In order to reduce the need for Day 15 visits, Investigators should:
 
 • Consider switching all patients who are on the Q2 week 240 mg nivolumab regimen to the Q4 week 480 mg regimen instead, as possible. • Start all newly enrolled patients on the Q4 week 480 mg regimen.
Day 15 Sample Collection for PK and Other Exploratory Tests (for Cohorts 1 through 8)	
In order to eliminate the Day 15 clinic visit (for Cohorts 1 through 8):
 
 • C1D15 PK samples, PD samples (TCR sequencing, flow cytometry, protein and cytokine biomarkers), and triplicate ECG may be collected at C2D1 instead. • C2D15 PD samples (flow cytometry, protein and cytokine biomarkers) may be collected at C3D1 instead.

Assessment/Procedure	Change During COVID-19 Pandemic
PK Sample Collections	For Cohorts 1 through 8: 
 • The PK collection required post-dose at 7 hours (5-9 hours) on C1D1 and C1D15 may not be collected in order to reduce the time that patients need to remain in the clinic for the blood draw and ECGs. For dose expansion portion of Cohort 9 and Cohort 10: 
 • The PK collection required post-dose at 7 hours (5-9 hours) on C1D1 and C2D1 may not be collected in order to reduce the time that patients need to remain in the clinic for the blood draw and ECGs.
PK sub-study for patients with renal impairment (for Cohorts 1 through 8)	Temporarily suspended for new patients to reduce the time patients need to remain in the clinic or hospital for blood draws.

Action and Reporting in the Event of Documented or Suspected COVID-19 Infection

Study Treatment

- Patients in Screening for Study Entry – Patients who exhibit symptoms consistent with COVID-19 infection or have recent COVID-19 test results consistent with active viral replication should delay study entry and start of study treatment until resolution of symptoms and evaluation by the Investigator. Questions should be directed to the Sponsor’s Medical Monitor.
- Patients in Study Treatment – For patients on study treatment exhibiting symptoms consistent with COVID-19 infection, contact the Sponsor’s Medical Monitor as soon as feasible.

3.0 Purpose

The statistical analysis plan (SAP) describes the statistical methods to be used during the reporting and analyses of data collected under Mirati Therapeutics, Inc Protocol 516-003.

4.0 Scope

This plan is a living document that supplements the study protocol for statistical analysis-related aspects.

The SAP outlines the following:

- Study objectives and endpoints
- Study design
- Analysis populations
- Endpoint and variable definitions
- Data handling
- Data review
- Statistical methods

Deviations from the statistical analysis plan will be described in the Clinical Study Report (CSR).

5.0 Introduction

This SAP describes the statistical methods to be used during the analysis and reporting of data collected under Mirati Therapeutics, Inc. Protocol 516-003.

This SAP should be read in conjunction with the study protocol and case report form (CRF). This version of the plan has been developed using the protocol version 4.0 dated 22 June 2020 and CRF version 5.0 dated 29 Oct 2020. Any further changes to the protocol or CRF may necessitate updates to the SAP.

The SAP will be developed in two stages. An initial SAP, known as the SAP, will be finalized based on the current protocol and CRF, so that programming may be created. Changes following approval of the SAP will be tracked in the SAP Change Log and an amended SAP will be finalized prior to database lock.

6.0 Study Objectives and Endpoints

6.1 Objectives

6.1.1 Primary Objective

- To evaluate the clinical activity of sitravatinib in combination with PD-(L)1 checkpoint inhibitor regimens in patients with advanced or metastatic urothelial carcinoma.

6.1.2 Secondary Objectives

- To evaluate the safety and tolerability of the combination regimen in the selected population.
- To evaluate secondary efficacy endpoints of the combination regimen in the selected population.
- To evaluate the pharmacokinetics (PK) of sitravatinib administered in combination regimens.
- To evaluate the PK of sitravatinib in patients with renal impairment, to be implemented in selected study sites contingent upon early results in the study or sitravatinib program.
- Cohort 9 only: To identify recommended Phase 2 combinatorial doses (RP2Ds) of sitravatinib, pembrolizumab and enfortumab combination treatment.

6.1.3 Exploratory Objectives

- To assess the effect of the combination regimen on circulating PD-L1, immune cell populations and cytokines.
- To assess the effect of the combination regimen on tumor cell PD-L1 expression, tumor infiltrating immune cell populations and gene expression signatures.
- To assess the correlation of tumor PD-L1 protein expression and gene alterations in circulation and in tumor tissue with treatment outcome.

6.2 Endpoints

6.2.1 Primary Endpoint

The primary endpoint is the Objective Response Rate (ORR) as defined by Response Evaluation Criteria in Solid Tumors version 1.1 (RECIST 1.1) as per local Physicians in all other Cohorts.

6.2.2 Secondary Endpoints

- Safety characterized by type, incidence, severity, timing, seriousness and relationship to study treatment of adverse events, and laboratory abnormalities.
- Secondary efficacy endpoints
 - Duration of Response (DOR)
 - Clinical Benefit Rate (CBR)
 - Progression-Free Survival (PFS)
 - 1-Year Survival Rate
 - Overall Survival (OS)
- Blood plasma concentrations of sitravatinib.
- Lead-in dose escalation portion of Cohort 9 only: Dose-limiting toxicities (DLTs).

6.2.3 Exploratory Endpoints

- Circulating PD-L1 concentration
- Circulating immune cell populations
- Circulating cytokine concentrations
- Circulating tumor deoxyribonucleic acid (ctDNA)
- T-Cell Receptor sequencing
- Tumor PD-L1 expression
- Immune cell populations in the tumor
- Gene expression signatures in the tumor
- Tumor gene alterations

7.0 Study Design

Study 516-003 is an open-label, Phase 2 evaluation of the investigational agent sitravatinib in combination with PD-(L)1 checkpoint inhibitor regimens in patients with locally advanced or metastatic urothelial carcinoma. The study will evaluate sitravatinib in combination with the PD-1 checkpoint inhibitor nivolumab, and sitravatinib in combination with the PD-1 checkpoint inhibitor pembrolizumab and

the antibody-drug conjugate (ADC) enfortumab. An initial lead-in dose escalation evaluation may be initiated followed by further evaluation of clinical activity in 2 populations if a tolerable dose regimen for this combination is identified.

The primary objective is to evaluate the clinical activity of the combination regimens using ORR in accordance with RECIST 1.1. Secondary objectives include evaluation of safety, secondary efficacy endpoints, PK of sitravatinib, and (for lead-in dose escalation portion of Cohort 9 (35mg, 70mg, and 100mg) DLTs for Cohort 9. The Schedule of Assessments to be performed in the study are presented in Table 1 and

. The schedule for collection of pharmacokinetic and pharmacodynamic samples and ECG assessment time points are presented in Table 2 and Table 4.

7.1 Initial and Contingent Study Cohorts

Initial cohorts will be used to refer to the first two cohorts (cohort 1 and cohort 2) in which patients with documented disease progression on or after checkpoint inhibitor therapy as the most recent treatment will be enrolled.

Contingent cohorts will be used to refer to one or more cohorts (cohort 3, 4 and up to cohort 9) that may be added to the study on a contingent basis. Cohorts 3 and 4 will enroll patients previously receiving treatment with selected immunotherapies, including anti-CTLA-4, anti-OX40 or anti-CD137 therapy. Cohorts 5 and 6 will enroll patients who have not previously received checkpoint inhibitor therapy (CIT-naïve). Cohort 7 will enroll patients with documented disease progression on or after a previous anti-PD-(L)1 and ADC (in combination or separately, and in any order), and who were previously treated with a platinum-based chemotherapy. Cohort 8 will enroll patients with documented disease progression on or after a previous anti-PD-(L)1 and ADC (in combination or separately, and in any order), and considered ineligible for platinum-based chemotherapy. Cohort 9 (including lead-in dose escalation) will enroll patients who have previously received a PD-(L)1 checkpoint inhibitor and a platinum-based chemotherapy.

7.1.1 Initial Study Cohorts

The initial study population will include patients with documented disease progression on or after a PD-(L)1 checkpoint inhibitor therapy as the most recent treatment [anti-PD-(L)1 refractory cohorts], stratified into 2 cohorts based on whether patients were previously treated with or ineligible for platinum-based chemotherapy, as depicted in Figure 1.

- Cohort 1: Patients with documented disease progression on or after previous anti-PD-(L)1 as most recent treatment, and who were previously treated with a platinum-based chemotherapy.
- Cohort 2: Patients with documented disease progression on or after previous anti-PD-(L)1 as most recent treatment, and considered ineligible for platinum-based chemotherapy.

Enrollment will occur in 3 stages. Stage 1 of enrollment will include a minimum of 9 evaluable patients in each cohort. Patients included in the evaluable population will have received treatment with both sitravatinib and nivolumab and have at least one on-study disease assessment prior to discontinuation. The exact stopping rules will be calculated based on the Predictive Probability Design (Lee-2008), once the exact number of patients evaluable at Stage 1 is known. With exactly 9 evaluable patients at Stage 1, if at least 1 patient has an Objective Response, 8 additional evaluable patients will be enrolled in the treatment cohort, for a total sample size of 17 evaluable patients. If at least 3 Objective Responses are observed in a treatment cohort, further investigation may be warranted. If Stage 2 results in a cohort are of high interest for efficacy (in terms of examining the risk benefit ratio and not only in terms of ORR), enrollment may be expanded to as many as 40 patients in total in that cohort to narrow the 95% Confidence Interval (CI) around the ORR point estimate and to further characterize the durability of disease control.

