Based on review of the AEs reported with sitravatinib in context of the mechanism of action, nonclinical data, frequency, and Investigator assessment of causality, the following AEs have been assessed as expected serious adverse drug reactions (SARs) for sitravatinib, or serious adverse events (SAEs) with at least a reasonable possibility of a causal relationship to sitravatinib administered as monotherapy or in combination with other agents: deep vein thrombosis/embolism/pulmonary embolism, diarrhea, ejection fraction decreased, fatigue, hypertension, nausea, PPE, and vomiting. Refer to the current IB for updated information during the course of the study.

Nonclinical toxicology studies as well as clinical safety data from the Phase 1/1b and Phase 2 studies suggest that AEs associated with sitravatinib are similar to those observed with other small molecule inhibitors of the VEGFR pathway.

Based on reported clinical experience with sitravatinib and similar agents, and nonclinical data with sitravatinib, guidance to the Investigator is provided for selected adverse events in Section 5.5.1.

1.3.3.3 *Sitravatinib Clinical Efficacy*

As of protocol Version 4.0, early clinical activity with the combination of sitravatinib and nivolumab in Study 516-003 is promising with multiple cohorts (Cohorts 1, 2, 3 and 5) having met the efficacy criteria per the PPD design to advance to Stage 2, and Cohort 1 having further advanced to the Expansion stage. Other cohorts are pending such decisions as enrollment progresses. As of 26 July 2019, updated data from an interim analysis of clinical activity from Cohort 1 at the time of expansion from Stage 2 to the Expansion stage of the PPD design, showed a preliminary objective response rate (ORR) of 27% among 22 clinical activity evaluable patients (Msaouel-2019). Cohort 1 has since completed enrollment and final efficacy updates including secondary efficacy endpoints are awaited. Similarly, early efficacy updates are awaited for the remaining active cohorts of Study 516-003.

Final efficacy results are awaited from both the Phase 1b segment of Study 516-001, and Study MRTX-500.

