7.1.5 Hypothesis and Sample Size Considerations

This Phase 2 study will use Predictive Probability Designs (Lee-2008) for initial cohort 1 and 2. In summary, Cohorts 3 and 4 will also use Predictive Probability Designs with the same assumptions as the initial cohorts (Section 6.1), Cohorts 5 and 6 will use Predictive Probability Designs with revised assumptions, Cohorts 7 and 8 will use confidence interval method with the revised assumptions, the lead-in dose escalation portion of Cohort 9 will use the mTPI-2 design (Guo-2017; Appendix 2).

In creating the statistical designs, the Type 1 error (α) is constrained to <0.05 and Power ($1-\beta$) is constrained to ≥ 0.90 .

7.1.5.1 Cohort 1 and 2:

ORR in accordance with RECIST v1.1 is the primary endpoint. The ORR using nivolumab in the population of advanced/metastatic urothelial carcinoma who experienced disease progression on or after treatment with a checkpoint inhibitor is assumed to be 5% (p_0); thus, this rate is considered uninteresting. The target ORR using sitravatinib in combination with nivolumab in this study population is 30% (p_1). Stage 1 of enrollment will include a minimum of 9 evaluable patients in each cohort. Patients included in the evaluable population will have at least one on-study disease assessment prior to discontinuation; patients who discontinue treatment due to adverse events or withdrawal of consent prior to the first on-study disease assessment will not be included in the evaluable population. With exactly 9 evaluable patients at Stage 1, if at least 1 patient has an Objective Response, 8 additional evaluable patients will be enrolled in the treatment cohort, for a total sample size of 17 evaluable patients. If at least 3 Objective Responses are observed in a treatment cohort, further investigation may be warranted. If the true ORR is 5% (null hypothesis), the probability of early termination during the study is 0.63; the Type 1 error is equal to 0.0466 and the power is equal to 0.9045.

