11.6 Efficacy Analyses and Efficacy Variables

11.6.1 Objective Response Rate (ORR)

Disease assessments involving radiographic evaluations may be performed over the course of a few days. The date of response (Complete Response, CR; Partial Response, PR; Stable Disease, SD; or Not Evaluable, NE) will be recorded as the date of the last radiographic evaluation included in the series for that time point assessment. The date of progression (PD) will be recorded as the date of the first radiographic evaluation included in the series for that time point assessment to identify progression.

ORR will be categorized in accordance with RECIST v1.1. (Appendix 3) Objective Response Rate (ORR) is defined as the percent of patients documented to have a confirmed CR or PR as defined in Table 9.

Descriptive statistics (frequency and percentage) for ORR, CR, and PR will be presented. The 95% exact Clopper-Pearson CI of these response rates will be calculated. An exact test for single proportion (two-sided $\alpha = 5\%$) will be performed to test $H_0: ORR \leq 5\%$ against $H_1: ORR > 5\%$.

Best overall response (BOR) is defined as the best response among all overall responses (in the order CR, PR, SD, PD, and indeterminate NE) recorded from the start of study drug until disease progression/recurrence, or start of anti-cancer therapy, whichever comes first.

The status of best response of CR or PR must be confirmed by repeat tumor assessment within no less than 4 weeks according to RECIST version 1.1. If the status of CR or PR cannot be confirmed by repeat tumor assessment, the BOR of unconfirmed CR and PR will be determined per RECIST 1.1. The status of BOR of SD requires an on-study assessment after at least 42 days on treatment. Patients without a valid clinical response assessment will be assigned a best overall response of NE. No response will be counted after PD.

Table 9 lists out the different scenarios of confirmed response based on subsequent assessment. The status of SD requires an on-study assessment at least 42 days on study. Patients without a valid clinical response assessment will be assigned a best overall response of NE.

Table 9 Confirmed Response Based on Subsequent Assessments*

First Time Point Response**	Second Time Point Response	Confirmed Response (Best Response)*
PD	No further evaluation	PD
NE	PD	PD
CR	PD	SD or PD (1)
PR	PD	SD or PD (1)
SD	PD	SD or PD (1)
CR	CR	CR
CR	NE **	SD or NE (2)
PR	CR	PR
PR	PR	PR
PR	SD (3)**	SD
PR	NE **	SD or NE (2)

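### Cohorts 1-4: once a cohort is expanded beyond Stage 2, its single pooled ORR includes the patients whose results opened the expansion, so it reads high if the true ORR is low

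*SAP*

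**What the plan says.** For Cohorts 1 and 2, and by reference Cohorts 3 and 4, SAP 7.1.1 and 7.1.5 set out three stages.

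- Stage 1: "With exactly 9 evaluable patients at Stage 1, if at least 1 patient has an Objective Response, 8 additional evaluable patients will be enrolled".
- Stage 2: the cohort continues "for a total sample size of 17 evaluable patients. If at least 3 Objective Responses are observed in a treatment cohort", further investigation may follow.
- Stage 3: if Stage 2 results are of high interest, "enrollment may be expanded to as many as 40 patients in total in that cohort to narrow the 95% Confidence Interval (CI" around the ORR. The other stated aim is to characterise durability of disease control.

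The Stage 3 trigger is a judgement. SAP 7.1.1 and Protocol 9.1 describe it as a risk-benefit view that goes beyond ORR. Protocol Section 3 names ORR together with the secondary efficacy endpoints. ORR is part of the trigger in each version.

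Protocol 9.3.1 makes the Stage 3 decision in the full analysis population. SAP 11.6.1 uses the same population for the primary ORR and states: "The 95% exact Clopper-Pearson CI of these response rates will be calculated". SAP Table 5 shows that interval for responses among all 40 patients. Neither document gives a summary by stage, an estimate that allows for the selection, or a caveat about it.

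**The concern.** A cohort reaches 40 patients only if its first 17 or so did well enough. Those patients stay in the final estimate, partly by construction with a favourable count, and are pooled with up to 23 patients who were not selected in this way. A Clopper-Pearson interval treats all 40 as a fixed sample.

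The ORR of an expanded cohort is the figure that will be compared with the 5% null and the 30% target. If the true ORR is well below the target, the pooled figure overstates activity, and the reader has no row of unselected patients to set beside it. Cohort 1 has already been through this step: Protocol 1.3.3.3 reports that data at the time of its expansion "showed a preliminary objective response rate (ORR) of 27% among 22 clinical activity evaluable patients".

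**Working it through.** **Inputs.** From SAP 7.1.5: the null ORR, for patients "who experienced disease progression on or after treatment with a checkpoint inhibitor is assumed to be 5" per cent, and "The target ORR using sitravatinib in combination with nivolumab in this study population is 30" per cent. From SAP 7.1.1: at least 1 of 9, at least 3 of 17, and up to 40 in total, so 40 - 17 = 23 further patients. From SAP 11.6.1: a two-sided 95% Clopper-Pearson interval, nominally at most 2.5% per tail.

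**Assumptions.** Expansion happens whenever the written rule is met, the cohort goes to 40, and the same patients and responses count at the decision and in the final analysis.

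**The plan's own figures.** P(stop at 9 | 5%) = 0.95^9 = 0.630. Exact enumeration of the two-stage rule gives P(pass | 5%) = 0.0466 and P(pass | 30%) = 0.9045. This agrees with the SAP, where "the Type 1 error is equal to 0.0466 and the power is equal to 0.9045" and early termination is 0.63. The five Table 5 intervals also reproduce.

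**Mean pooled ORR given expansion.** With X17 the responses among the first 17,

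mean = [E(X17 | rule met) + 23p] / 40.

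| True p | P(rule met) | E(X17 given met) | Mean pooled ORR | Bias (points) | P(lower limit > p, given expansion) |
|---|---|---|---|---|---|
| 5% | 0.047 | 3.21 | (3.21 + 1.15)/40 = 10.9% | +5.9 | 15.5% |
| 10% | 0.223 | 3.48 | (3.48 + 2.30)/40 = 14.5% | +4.5 | 5.8% |
| 15% | 0.456 | 3.83 | (3.83 + 3.45)/40 = 18.2% | +3.2 | 2.5% |
| 20% | 0.663 | 4.27 | (4.27 + 4.60)/40 = 22.2% | +2.2 | 2.9% |
| 25% | 0.812 | 4.80 | (4.80 + 5.75)/40 = 26.4% | +1.4 | 1.4% |
| 30% | 0.905 | 5.42 | (5.42 + 6.90)/40 = 30.8% | +0.8 | 1.6% |

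**Lower limit.** The last column sums the conditional distribution of responses among 40 over counts whose lower limit exceeds p. At a true 5% the limit is 4.2% for 5/40 and 5.7% for 6/40, so it is P(at least 6 of 40 | expanded) = 15.5%. Because counts are discrete, the error rises and falls between the tabulated points. Its worst value is 20.3% for a true ORR of 5-10%, 7.9% for 10-15%, 4.5% for 15-20%, 3.6% for 20-25% and 2.9% for 25-30%.

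**All outcomes together.** Count every cohort at the size it reached (9, 17 or 40). The lower limit then exceeds the truth at most 2.499% of the time for any true ORR from 2% to 60%. At a true 5%, the chance of expanding and also excluding 5% is 0.0466 x 0.155 = 0.7%. The mean reported ORR is too low, by 1.9 points at a true 5% and 1.6 points at 30%, because stopped cohorts pull it down.

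**Sensitivity to the bar.** A stricter informal bar of at least 5 of 17 gives a mean of 18.9% at a true 10% (lower-limit error 24.9%) and a bias of +3.0 points at 30%. With a decision at 22 patients (after at least 1 of 9, then 18 more) and a true 15%, the mean is 19.1% for a bar of at least 4 and 23.1% for a bar of at least 6.

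**The case against.** The strongest reply is that the design is sound as a whole. SAP 11.0 tabulates every cohort, expanded or not, so no selective reporting is planned. Over all outcomes the interval holds its error rate and the mean bias is downward. At the 30% target the conditional bias is under one point. This stands, and it limits the point to the figure read after expansion.

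The trigger is also not a pure response count. It takes in risk-benefit, and Protocol Section 3 lets unconfirmed responses start the expansion (with follow-up required to keep supporting it), while the reported ORR counts confirmed ones. Either could make the true bias smaller than tabulated. This stands as well.

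A reader might infer more than the documents support:

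- **That the lower limit is unreliable in general, or that Type 1 error is inflated.** Under the written rule the excess is material only given expansion and mainly below a true ORR of about 15%.
- **That Cohort 1 shows a bar of 6 of 22.** 27% of 22 is 6 responses, but that is an observed result. No bar is stated. At least 6 of 22 would pass with probability only 0.68 at a true 30%, whereas SAP 7.1.5 constrains the design to power of at least 0.90 and alpha below 0.05. At least 4 of 22 meets both (alpha 0.020, power 0.909).
- **That most of Cohort 1's final patients are those who opened the expansion.** Its final size is not given, 40 is a ceiling, and the 22 are clinical activity evaluable patients, whereas the primary ORR uses the full analysis population.
- **That expansion rests largely on response counts.** Neither document weights the components of the decision.

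**Conclusion.** The point holds in limited form. The plan pools the patients who opened an expansion with those enrolled afterwards and reports one unadjusted ORR and interval. Given expansion under the written rule, the estimate is biased upward by about 6 points at a true 5%, 4.5 at 10%, 3 at 15%, 2 at 20% and under 1 at 30%. The lower-limit error is clearly above nominal at 5% and 10%, and close to nominal at 15% to 30%.

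These sizes rest on expansion whenever at least 3 of 17 respond, stage sizes of 9, 17 and 40, and the same responses counting at both times. The actual trigger is discretionary and stage sizes can differ, as Cohort 1's 22 show, so the real bias may be smaller or, with a stricter informal bar, larger. The primary analysis need not change. What is missing is a supportive row free of the selection and a label on the pooled figure.

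**What to change.** Keep the pooled ORR as primary and add to SAP 11.6.1:

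> For any cohort expanded beyond Stage 2, ORR with exact 95% CI will also be reported as a supportive analysis for patients enrolled after the documented expansion decision, and the pooled ORR will be footnoted as including the patients on whom that decision was based.

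Record the decision date for each expanded cohort. SAP 10.0 already has enrolment decisions documented, and SAP 5.0 provides for an amended SAP before database lock.

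The cost is one table row and one footnote per expanded cohort, from data already collected. The downside is precision: the supportive interval rests on at most 23 patients under the planned rule. For example, 5/23 is 21.7% with a 95% CI of 7.5% to 43.7%. It therefore belongs beside the pooled figure and does not replace it.

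An estimator that conditions on expansion would use all 40 patients (8/40 would become 17.6% in place of 20.0%), but it needs a fixed numerical trigger, which the plan does not have. The split by decision date does not.
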